collected for our study will be kept strictly confidential and will never be reported to clinic staff or anyone outside the study team. We will also make clear to women the potential risks to being in the study, including the potential for increased risk of violence if associated with being part of a study. It will also be explained to the participant that they are also able to include their/a current male partner to participate in the study with them if they are randomized to the intervention arm and why this might be beneficial. Details of partner inclusion in the study are described next. Because inclusion in the study requires being able to send appointment reminders and questions to assess the safety of participants, contact details including a cell phone number that the participant can access safely to receive study messages and reminders will be collected and checked. After explaining the study, the study staff member will allow time for questions. They can take as long as they like and can return at another time to complete the process.

g. Qualitative component consent

For the FGDs and in-depth interviews with both recipients of care and providers, a separate information sheet and consent form will be administered by a study interviewer. We will make it clear to the study participant that this qualitative exploration activity is voluntary and that, if they decide to not participate in the FGDs and/or IDIs, it will not influence anything in the study or their follow up assessments or any aspect of their healthcare, and will not affect their work at the healthcare facilities as healthcare providers.

h. Male Partners

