Texts on IPV may be altered to avoid risk if there is concern that a partner or other perpetrator of violence might pick up this message (for example we may say “Please type Yes if there is any issues you need help with”). These same questions are asked weekly for all study participants (not just those receiving CETA). If all the responses are no, the study staff will do nothing. If any of the responses are yes, the study staff, who will be trained in safety planning, will telephone the participant to ask additional safety questions to assess risk. If the study staff member determines there is minimal risk, a telephone safety contract will be completed. This involves asking the participant to “promise” to keep themselves safe and alive for the next 7 days. If the study staff member decides the participant needs further evaluation or requires assistance, they will phone a CETA supervisor who will call the participant and complete safety planning. CETA supervisors are more trained in safety assessment and planning and will assess, and if needed, plan to meet the participant to assure safety. A supervisor will either speak directly with the client or even travel to their home should there be imminent danger. Johns Hopkins PI, [name], wrote a seminal paper on integrating safety planning within LMIC programs regardless of location or availability of professionals – and has successfully delivered this in multiple programs and trials(77). If there is no response we would text again and if still no response we could call. If a patient has previously shown signs of distress, we would attempt a home visit where safe and possible, otherwise the patient will be considered lost to follow up. As the clinic already has protocols for supporting admission to the hospital or referral for services for distressed patients and they already

have strong links to the hospital providers, we will work with the clinic staff to ensure distressed participants get the care they need.

We will be ensuring that study participants have their own phones to enhance safety. The sharing of phones and potential for others to read messages will be discussed when we agree how to send messages to participants. Male participants will require a phone that receive texts as they will follow the same protocol as the women participants for safety concerns (i.e. suicidal thoughts, homicidal thoughts and victimization of IPV).

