Some risk is due to the assessment measures inherent in any mental health care with questions asking about thoughts, feelings, and personal difficulties that may be private (e.g., alcohol, substance use, trauma-related or depressive symptoms). Risks also include possible embarrassment, distress, or inconvenience related to questions regarding personal information and mental health problems. Assessment measures of mental health symptoms include items regarding suicidal or homicidal ideation, and disclosure of traumatic events inclusive of abuse. By US and local ethics standards, reports of suicidal and/or homicidal ideation also ethically require follow-up by the counselors and investigators, and could potentially result in the need to violate confidentiality in order to protect the participants and their families. Thus, this represents a potential limit to confidentiality. For this and other reasons, possible breaches of confidentiality also pose a potential risk in the proposed study. Our team has published specifically on developing safety protocols in low-resource settings and has implemented these in previous work. Still, each of these risks is carefully considered below.

c. Assessment of Safety and Data Safety Monitoring Plan (DSMP)

Adverse Events. The PIs will be responsible for oversight of potential adverse events. An adverse event (AE) is any untoward medical occurrence in a subject during participation in the study. We anticipate two potential types of AEs that could be directly related to study participation. These include distress experienced with regard to research participation and breach of confidentiality and privacy. With regard to both matters, we have protocols in place that include conferring with the PIs or a project mental health provider and appropriate safeguards to reduce risk of breach of confidentiality and privacy (see Human Subjects plan). We anticipate that AEs related to suicidal ideation and/or intent, homicidal ideation and/or intent, clinical worsening necessitating a higher level of care, and neglect/abuse may come to the attention of study staff during the consenting and during provision of care. We note that given the study population, it is anticipated that some women will continue to experience violence and suicidal ideation. Further given the population includes women who are not virally suppressed on the HIV treatment, some deaths may occur due to HIV.

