Psychological risks for participants posed by the research may be related to the sensitivity of some of the measures. Items include thoughts, feelings, and personal difficulties that may be private, such as acts of violence and/or symptomatology related to common mental health problems and/or substance use. Risks also include possible embarrassment, distress, or inconvenience related to questions regarding personal information and mental health problems. Assessment measures of mental health symptoms include items regarding suicidal or homicidal ideation, and disclosure of traumatic events inclusive of sexual and physical abuse commonly experienced by violence-affective populations. By US and local ethics standards, reports of suicidal and/or homicidal ideation also ethically require follow-up by the counselors and investigators, and could potentially result in the need to violate confidentiality in order to protect the participants. Thus, this represents a potential limit to confidentiality. For this and other reasons, possible breaches of confidentiality also pose a potential risk in the proposed study. There is a risk that the interventions (CETA; mHealth + safety) will not be efficacious for some individuals or that the interventions could lead to a worsening of symptoms. The Johns Hopkins PI ([name]) has published specifically on developing safety protocols in low-resource settings and has implemented these in her 15+ years of work in multiple low resource settings. Still, each of these risks is carefully considered below.

g. Emotional distress protocol

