Some participants may experience emotional distress as a result of responding to the assessments or receiving feedback. We will take multiple measures to minimize this occurrence. First, study staff and counselors will be trained in responding to distress. Second, multiple levels of back-up support will be developed for our study staff. [name] will train supervisors as part of the CETA training who will receive thorough training in clinical matters such as identifying levels of distress, local referral options and processes, and clinical interviewing on sensitive topics. Our team will also be able to contact [name] (a clinical psychologist) who has worked closely with the clinical psychologists at the hospital where the clinic is based if required. Finally, in the event that an individual is experiencing significant distress, the local research team can consult with [name]. The instruments in this study have been used by the JHU team in several projects in LMIC, without undue distress occurring. All participants will also be told that they can refuse to answer any questions and still participate in the project.

It is also possible that the participants could become distressed by participation in the interventions, CETA or mHealth + safety checks. Many therapeutic interventions like CETA deal with small degrees of stress within a session as part of the treatment. Based on research and experience, the expected degree

of distress will be minimal and therapeutic rather than harmful. In cases where distress does occur, the participant would be with a trained counselor who is skilled at handling such situations. In addition, these counselors will have local supervisors, [name], and supervision from [name] (MPI; Clinical Psychologist) as needed. In addressing safety, there can be some distress in planning for preventing suicide. Again, the research is strong that this is life-saving and therapeutic rather than harmful.

For those participants selected to participate and enrolled in the qualitative phase of study who may become distressed during the FGDs and IDIs when they are asked to recall their experiences with CETA, we will follow the same distress protocol that is described above. Data collection for those sessions will pause or stop as needed and support provided. [name] will again be on hand to provide clinical support and guidance and clinic referral processes will be followed as needed.

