To ensure confidentiality and minimize the risk of accidental disclosure of sensitive information during the qualitative phase of this study, all individual interviews with participants will be conducted in a private area or room designated for this purpose at location that is convenient for the participant. For the focus group discussions, we will explain the importance of confidentiality and request that the

participants use a nickname or made-up name that is not their own and that they do not share what they have heard in the group session with anyone outside of the group. However, we cannot guarantee that they will not share the information and this will be made clear during the consent process.

i. Violations of Confidentiality

There is always the possibility of an accidental breach of confidentiality when conducting research. Further because data will be linked between women and any included partner, breach of confidentiality of one partner could reveal inclusion of the other partner. While this is acknowledged, we feel there is a very low likelihood of this occurring because of the precautions that will be taken to protect confidentiality and based on our experience conducting trials among HIV- and IPV-affected families. Disclosure of significant social problems such as intimate partner violence, may result in negative stigma being associated with the individual and/or family, fear of imprisonment of a family bread-winner who is a perpetrator, and other such problems. Domestic violence disclosure may result in unwanted intervention and consequences for the individual responsible. Our team has over a decade of experience specifically working with youth and families that experience abuse and violence and believe that the benefits of these issues coming out far outweighs the risks inherent in violence and abuse situations. We also believe we have established an effective method to reduce this risk.

j. Violence Reports

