Subjects will be protected against the risk and repercussions of accidental disclosure of HIV status and other confidential information, in several ways. First, all study data will be de-identified. That is, it will contain only a unique study ID number. The link between the ID and the participant’s identifying information will be kept in a password protected database in a locked office in South Africa. We also note that given some participants may choose T-CETA, the risk of disclosure of being in the study may increase if they were overheard and as such we will work with participants to ensure they are in a safe and private location for any T-CETA sessions. To protect against other violations of confidentiality, study staff will be trained in expectations that they are not to disclose any information collected in the study to anyone outside the study team. All study staff will be trained in human subjects’ research and required to pass an ethics certification course and receive training in Good Clinical Practices. All participants will be encouraged to contact the local study coordinator, local investigators, or other staff to report any undesirable conduct associated with the study. These reports will be brought to the attention of the study coordinator, local PI and co-Is and the MPIs, and appropriate steps will be taken to solve the problems, including reporting to the ethical review boards.

d. Interpersonal Violence Disclosures

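### The full-consent assurance and the staff non-disclosure rule carry no safety exception, although two other sections say suicidal or homicidal risk may require breaking confidentiality

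*Combined protocol and SAP*

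**What the plan says.** Four passages of the combined protocol and SAP bear directly on this.

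- **Study Procedures, f. Full Consent.** Women are to be promised that information "collected for our study will be kept strictly confidential and will never be reported to clinic staff or anyone outside the study team". No exception follows. The next sentence promises to explain the risks of taking part, "including the potential for increased risk of violence if associated with being part of a study", and names no other.
- **Adequacy of Protection Against Risks, c. Disclosure of HIV, violence/abuse, or other confidential information.** Staff are trained that "they are not to disclose any information collected in the study to anyone outside the study team". Again there is no exception.
- **Data Safety and Monitoring Plan, b. Trial Safety.** Reports of suicidal or homicidal ideation require follow-up and could lead to "the need to violate confidentiality in order to protect the participants and their families".
- **Ethical Considerations, f. Potential Risks.** Nearly the same sentence appears, ending "in order to protect the participants. Thus, this represents a potential limit to confidentiality".

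Other sections plan contact beyond the team. Study Procedures, i. Safety for both arms, says "we will work with the clinic staff to ensure distressed participants get the care they need". Secondary outcome data (Data Sources and Management, c) provides for referring control-arm women found to have serious mental health problems. Ethical Considerations, k. Suicidal intent, allows referral to a hospital psychiatrist. Adequacy of Protection, e. Suicidal intent, allows a round-the-clock watch by people from the community.

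**The concern.** Followed to the letter, Full Consent gives women a promise that the protocol elsewhere says may have to be broken. It also names clinic staff specifically among those who will not be told. The staff rule tells trained personnel to do something the safety sections may require them not to do. A participant should know the limits of confidentiality before she answers questions about suicide or homicide, and staff should work from one rule. At stake are the accuracy of what the protocol says women were told and the clarity of the instruction to staff. No estimate or test depends on it.

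**Working it through.** No figure in the plan is involved, so the check compares the texts.

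1. **Does the unqualified rule cover the answers that trigger the limit?** Yes. Full Consent and the staff rule both refer to information collected for or in the study. Trial Safety and Potential Risks tie the limit to assessment measures that contain items on suicidal or homicidal ideation. Those answers are study data.

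2. **Does either unqualified passage carry the exception?** No: 0 of 2. Two passages state the limit, both conditionally, as something that could arise. Neither says that participants will be told of it.

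3. **How far does the conflict reach?** Three things fall outside it:
   - Escalation to a supervisor, psychologist or investigator, which stays inside the team (Ethical Considerations, k; Adequacy of Protection, a and b).
   - Referral that the woman accepts.
   - Reporting violence to officials, which remains her decision (Ethical Considerations, j. Violence Reports).

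   What remains is disclosure outside the team, because of suicidal or homicidal risk, to which she has not agreed. Trial Safety and Potential Risks foresee this case when they speak of violating confidentiality. The planned contacts with clinic staff, psychiatry and community members show who might be told. They do not by themselves show disclosure without agreement, so they sit poorly with the assurance but do not prove the conflict.

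4. **Is the qualitative phase part of the contradiction?** No. Study Procedures, g. Qualitative component consent, makes no absolute promise. Ethical Considerations, h, says of other focus group members that "we cannot guarantee that they will not share the information and this will be made clear during the consent process". It names that limit and not the safety limit, which is an omission from a summary rather than a conflicting rule. The Emotional distress protocol says of these sessions that "clinic referral processes will be followed as needed".

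5. **Planned sizes.** Full Consent was written for 400 women. From the Overview of Study Design, the qualitative phase involves 3 × 6 = 18 to 3 × 10 = 30 women in groups, plus 0 to 10 interviewees not already in a group. That gives 18 + 0 = 18 to 30 + 10 = 40 women, the upper end matching the 40 in the qualitative sample size section. These are planned sizes, not numbers affected. The documents give no rate of disclosure without agreement, and none is assumed.

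**The case against.** The best reply is that Full Consent promises to explain risks and gives increased violence only as an example. The confidentiality limit sits in a section headed Potential Risks, so it could be among the risks explained. That is a fair reading of the risk sentence, but it leaves the assurance just before it unqualified.

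A second reply is that the consent forms are outside the review copy and may state the limit. This stands as far as the forms go, and nothing is claimed here about their content. The conflict lies in protocol text that can be read.

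A third is that the staff rule sits in a section that opens on accidental disclosure, while specific safety instructions govern risk events and staff are trained separately on disclosures and suicide risk. That lowers the practical consequence. The sentence itself still covers any study information and anyone outside the team.

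Three stronger readings are tempting and not supported:

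- **That women were misinformed at consent.** This cannot be known without the main form.
- **That help would be delayed.** The first step is a supervisor inside the team, and the safety sections call for immediate action.
- **That the qualitative-phase consent breaks a promise.** The protocol makes no such promise there. That phase also excludes women with a suicide attempt, ideation with intent and plan, or self-harm in the past month.

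**Conclusion.** The inconsistency is real and minor. Full Consent's assurance and the staff rule contradict the limit stated in Trial Safety and Potential Risks, for the narrow case of disclosure outside the team for suicidal or homicidal risk without the woman's agreement. Only Full Consent uses the word *never*; the staff rule has the same content without it.

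Power and the primary analysis are unaffected. Roles and Responsibilities in the monitoring plan records that all one-year follow-ups are complete, so main-trial consent is over and the point there concerns the record. Looking forward, it bears on the staff rule and on the form used for the qualitative phase.

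The conclusion rests on reading the assurance as covering questionnaire and safety answers, which the text supports, and on no assumption about the consent forms.

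**What to change.** 1. **Full Consent and the staff rule:** add to each an exception such as *except where needed to protect the participant or another person from serious harm (suicidal or homicidal risk), or where she agrees to be referred for care*. Leave Violence Reports unchanged.
2. **Main consent form:** check it before writing anything about what was explained. If it carried the limit, say so in Full Consent. If it did not, record the discrepancy. Adding the statement without this check could make the record false.
3. **Qualitative-phase form:** confirm that it carries the limit before further use, and correct it if not.
4. **Optional:** name the safety limit beside the group-sharing limit in Ethical Considerations, h, for alignment.

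The cost is two short edits, a third if wanted, and two form checks. The protocol names four review bodies (Witwatersrand, Boston, Columbia and Johns Hopkins), so the edits and any form correction would presumably go to them as a small amendment. No new data are collected and the analysis does not change.

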4. LifeLine South Africa have a dedicated 24/7 counselling line for victims of IPV/domestic violence/gender abuse (<http://lifelinesa.co.za/>)
5. SheConquers SA also has support hotlines for women experiencing violence (<http://sheconquerssa.co.za/emergency-connect/>)

To maintain a safety net during the study, we will send three suicide questions and one IPV safety question via SMS weekly during the intervention period (3 months). These questions are:

- 1) “Are you thinking of killing yourself?”
- 2) “Do you have a plan to kill yourself?”
- 3) “Do you have the means to kill yourself?”
- 4) “Are you at risk of serious injury or death from interpersonal violence?”

We note that the last question will not be sent to male partners, only to women. We can also provide cell phones to those enrolled (regardless of arm) if they do not have their own, though as this is an inclusion criteria, this would only likely happen if a woman lost her phone during the course of the study. Questions can also be modified, working with the study participant to ensure that the question is disguised.

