- suggests that the research places subjects or others at a greater risk of harm (including physical, psychological, economic, or social harm) than was previously known or recognized.

Possibly related means there is a reasonable possibility that the incident, experience, or outcome may have been caused by the procedures involved in the research

Unexpected means the nature, severity, or frequency of the event is not consistent with either:

- the known or foreseeable risk of adverse events associated with the procedures involved in the research that are described in (a) the protocol-related documents, such as the IRB-approved research protocol, any applicable investigator brochure, and the current IRB-approved informed consent document, and (b) other relevant sources of information, such as product labeling and package inserts; or
- the expected natural progression of any underlying disease, disorder, or condition of the subject(s) experiencing the adverse event and the subject's predisposing risk factor profile for the adverse event.

AEs will be classified by severity (mild, moderate, or severe) depending on the intensity of the event on the patient. An AE will be "mild" if it does not have a major impact on the patient, "moderate" if it causes some inconvenience, and "severe" if it causes a substantial disruption to the patient's well-being. A severe AE is distinct from a serious adverse event (SAE), which is any AE that is medical and results in death, a life-threatening event, inpatient hospitalization, disability, congenital anomaly or birth defect,

and/or an important medical event based upon appropriate medical judgment. AE's and SAE's will also be classified according to the likelihood that they are related to the study intervention (CETA or Control).

Safety Review

Both the risks listed below and unknown risks will be monitored as follows:

1. The risks that will be monitored in this study are 1) intimate partner violence episodes; and 2) new onset suicidal or homicidal ideation.

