Assessments and Intervention: All participants will be directly asked a set of questions each week during the active treatment phase (first 3 months after baseline) to assess suicide and homicide risk, and IPV. For CETA participants, this will be done during CETA sessions. For control participants, this will be via a mobile safety survey. The primary outcome of the proposed study is retention in HIV care and suppression by 12 months. Therefore, we want to minimize research contacts with participants as much as possible. We must balance that research aim, however, with the need to clinically monitor our study participants for safety. If a participant indicates any level of risk of harm to themselves, others or are being hurt by someone else, the study staff will immediately follow the locally developed safety protocol described above. In the active control, if the participant does not respond within 24 hours to the mobile safety survey, a staff member will call them and/or do a home visit when possible (though this has to be balanced against safety of staff) to assure response to safety questions. Study staff will be trained in how to recognize and respond to distress that may occur during the intervention and will call their supervisor if they are unsure of how to handle the situation.

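### The scripted weekly violence text sets a higher threshold than the risk the plan says it monitors and the trigger it states, so control women have no clearly scheduled weekly capture of lesser IPV while CETA women do

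*Combined protocol and SAP*

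**What the plan says.** **What is monitored.** The Data Safety and Monitoring Plan (section c, Safety Review, item 1) states: "The risks that will be monitored in this study are 1) intimate partner violence episodes". It gives no severity threshold.

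**What triggers action.** Adequacy of Protection Against Risks (section b, Safety) says all participants are asked weekly, for the first 3 months, about suicide and homicide risk and IPV. It starts the safety protocol as follows: "If a participant indicates any level of risk of harm to themselves, others or are being hurt by someone else".

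**What is sent.** Study Procedures (Safety for both arms) scripts four weekly texts, three on suicide and one on violence. The violence text reads: "Are you at risk of serious injury or death from interpersonal violence". On the replies: "If all the responses are no, the study staff will do nothing". The text may be disguised or replaced by a generic prompt asking whether help is needed with anything.

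**By arm.** Safety for both arms says the same questions go to everyone each week. It adds that CETA women are asked weekly about their IPV situation and have their safety plan updated. Section b, Safety, says instead that the weekly questions are put in session for CETA women and by mobile survey for controls.

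**Men.** Safety for both arms says of male partners that "they will follow the same protocol as the women participants for safety concerns (i.e. suicidal thoughts, homicidal thoughts and victimization of IPV". The same section says of the violence text: "We note that the last question will not be sent to male partners, only to women".

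**The concern.** The question asked, the event said to be monitored and the trigger for action are three different things. The text asks for a woman's own judgement that she is at risk of serious injury or death, from interpersonal violence generally. The monitored risk is an episode of partner violence. The trigger is any level of risk, or being hurt. A woman who was hit that week but does not feel in danger of serious injury or death can truthfully answer no, and the texting procedure then asks nothing of staff. This can happen even if every text is answered.

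The gap is not the same in both arms, because CETA women have a second and broader weekly enquiry. The DSMB was to review serious adverse events by arm each quarter and, on concern, the violence data from all participants weekly (Safety Review, item 4). If reports from all sources are pooled, equal true rates could look like an excess under CETA. If only the scripted text is used, a real difference below its threshold would not show.

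**Working it through.** The plan states no figure on this point, so there is nothing to reproduce. The check compares the passages.

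| Element | Place | Content | Severity floor |
|---|---|---|---|
| Monitored risk | DSMP c, Safety Review item 1 | IPV episodes | none |
| Trigger | Adequacy of Protection, b. Safety | any level of risk of harm, or being hurt | none |
| Scripted weekly text | Safety for both arms | self-judged risk | serious injury or death |
| Generic rewording | Safety for both arms; b. Safety | any issue needing help | none, and not specific to violence |
| CETA weekly enquiry | Safety for both arms; b. Safety | the IPV situation, in session | none |
| SVAWS, both arms | Data Sources, section a | frequency of recent IPV, 46 items; baseline, 3 and 12 months | none, but not weekly |

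**Step 1: threshold.** The scripted text is the only one of the first three rows with a severity floor. The stated trigger can be met while all replies are no.

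**Step 2: by arm.** Below that floor, a CETA woman still has the session enquiry. A control woman has the generic prompt if it was used for her, and otherwise nothing clearly scheduled each week.

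**Step 3: when the rewording applies.** Safety for both arms allows it where a partner or other perpetrator might see the message. Section b, Safety, allows it where a partner is not involved or has not discussed IPV. No men take part in the control arm, so the second condition could cover control women generally. The documents do not say how often either wording was to be used, so a yes need not mean the same thing from one woman to the next.

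**Step 4: mode.** One passage sends the same texts to everyone, while the other asks CETA women in session and controls by mobile survey. If the second is what happened, the two arms may share no weekly item at all.

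**Step 5: size.** Let *s* be the share of IPV episodes that meet the scripted threshold, and *c* the share captured in CETA sessions. The documents give neither, so both are assumed. The scripted text misses 1 − *s*. With equal true rates and all sources pooled, the apparent CETA:control ratio is max(*c*, *s*)/*s*.

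| Assumed *s* | Missed, 1 − *s* | Ratio at *c* = 50% | Ratio at *c* = 90% |
|---|---|---|---|
| 10% | 90% | 5.0 | 9.0 |
| 25% | 75% | 2.0 | 3.6 |
| 50% | 50% | 1.0 | 1.8 |
| 75% | 25% | 1.0 | 1.2 |

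For example, at *s* = 25% and *c* = 90% the ratio is 0.90/0.25 = 3.6. A span from 1.0 to 9.0 shows the direction the bias could take. It does not estimate its size.

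**The case against.** The strongest reply is that the text is a safety net, not an episode counter. Its threshold broadly fits one reporting rule, under which severe increases in IPV go to the DSMB, and continuing violence is expected in this population. Participants are also to be asked about increases they attribute to the study. This explains the wording, but it does not remove the conflict: Safety Review item 1 says episodes, and section b, Safety, says any level of risk. The timing of the question on study-related increases is not given.

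Interpersonal Violence Disclosures (Adequacy of Protection, section d) adds an offer, at check-ins, of help to report any current or past violence. That has no severity floor, but the passage does not make clear which check-ins it means. This is why the gap is described as no *clearly scheduled* weekly capture, rather than none.

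Several stronger readings are tempting, and the documents do not support them:

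- A reader might infer that this text is the trial's only weekly violence question. It is not, because CETA women are asked in session.
- A reader might infer that most IPV episodes draw a no. That needs *s* below 50%, and no severity mix is given.
- A reader might infer that these episodes go uncounted, or that the conclusion on whether CETA changes violence rests on the text. The SVAWS measures recent IPV in both arms at 3 and 12 months and is analysed by arm in mixed models. Nor do the documents define the DSMB's violence data as the text replies.
- A reader might want to express the gap as lost power. Event rates would have to be invented, for a test the plan never proposes. A per-episode share also cannot be applied to women: with four independent episodes (assumed), 30% capture per episode becomes 1 − 0.7⁴ = 76% per woman.
- A reader might infer that men have no other weekly contact. They complete the Client Monitoring Form at each session, so the conflict over men is real but small.

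Finally, the intervention is over and DSMB review of the main study closed in March 2025. The texts already sent cannot be changed.

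**Conclusion.** The concern holds as an inconsistency in weekly safety monitoring. The scripted violence text cannot by itself deliver the monitoring of IPV episodes, or the trigger, that the plan states. The shortfall falls on control women, because CETA women have a broader weekly enquiry. The passages also conflict on mode by arm and on male partners.

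The consequence is unequal ascertainment of violence reports between arms. If reporting is otherwise equal and all sources are pooled, the bias runs toward an apparent excess under CETA. Its size cannot be computed, since it depends on the severity mix of episodes, how often the generic text was used, and how CETA women were actually asked.

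The efficacy conclusion on violence is not affected, because it rests on the SVAWS. With the intervention and DSMB review complete, the point now bears mainly on how safety is reported.

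**What to change.** 1. **Reconcile the text.** Safety for both arms, Safety Review item 1, and section b, Safety, should agree on what is asked, of whom (including male partners), by which mode, when the generic wording applies, and what triggers action. Which threshold is right is a clinical decision and is not proposed here.
2. **Label the datum.** In the final safety tables, describe the weekly text reply as self-judged risk of serious injury or death, or as a reply to the generic prompt where that was used. It should not be called an IPV episode.
3. **Separate the sources.** Report disclosures in CETA sessions on their own line, apart from text replies.
4. **Limit the comparison.** Base any by-arm statement on violence on sources common to both arms: the SVAWS, and the common text item if the records show that both arms received it.

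The cost is a clarification of protocol wording or a note in the final report, one slightly longer safety table, and a more limited safety statement. No new participant contact is needed.
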